### 5.1 Evaluation of Best Overall Response

The best overall response is the best response recorded from the start of the treatment until disease progression/recurrence (taking as reference for progressive disease the smallest measurements recorded since the treatment started). The patient's best response assignment will depend on the achievement of both measurement and confirmation criteria.

Summary of the RANO Response Criteria (Adapted from (Wen, et al. 2010).

Criterion	CR	PR	SD	PD
T1 gadolinium enhancing disease	None	≥ 50% ↓	< 50% ↓ but < 25% ↑	≥ 25% ↑*
T2/FLAIR	Stable or ↓	Stable or ↓	Stable or ↓	↑*
New lesion	None	None	None	Present*
Corticosteroids	None	Stable or ↓	Stable or ↓	NA ‡
Clinical status	Stable or ↑	Stable or ↑	Stable or ↑	↓*
Requirement for response	All	All	All	Any*

Abbreviations: RANO, Response Assessment in Neuro-Oncology; CR, complete response; PR, partial response; SD, stable disease; PD, progressive disease; FLAIR, fluid-attenuated inversion recovery; NA, not applicable.

\* Progression occurs when this criterion is present.

‡ Increase in corticosteroids alone will not be taken into account in determining progression in the absence of persistent clinical deterioration.

NOTE: Patients may continue on treatment and remain under close observation and evaluation at 4-8 week intervals if there is uncertainty regarding whether pseudoprogression may be present as determined by the investigators. If subsequent radiographic or clinical assessments suggest that the patient is in fact experiencing progression, then the date of progression should be the time point at which this issue was first raised. Similarly, stable disease may be assigned in cases of presumed “pseudoprogression” associated with decreased steroid use.

## 5.2 Duration of Response

**Duration of overall response:** The duration of overall response is measured from the time measurement criteria are met for complete response (CR) or partial response (PR) (whichever is first recorded) until the first date that recurrent or progressive disease is objectively documented (taking as reference for progressive disease the smallest measurements recorded since the treatment started).

The duration of overall CR is measured from the time measurement criteria are first met for CR until the first date that progressive disease is objectively documented.

**Duration of stable disease:** Stable disease is measured from the start of the treatment until the criteria for progression are met, taking as reference the smallest measurements recorded since the treatment started, including the baseline measurements.

## 5.3 Neurological Exam and Performance Status

Patients will be graded using the KPS scale and their neurological function evaluated as improved, stable or deteriorated in addition to objective measurement of tumor size. These parameters will be used to determine the overall response assessment.

#### **5.4 Progression-Free Survival**

PFS is defined as the duration of time from start of treatment to time of progression or death, whichever occurs first.

### **6.0 DOSE MODIFICATIONS**

#### **6.1 Temozolomide Dose Modifications**

TMZ dosage modification is at the discretion of treating physician as per routine clinical care.

#### **6.2 Disulfiram Dose Modifications**

If a patient experiences any grade 2 or higher non-hematologic toxicity considered by the investigator to be possibly, probably, or definitely related to DSF, the dose of DSF may be decreased by 50% (i.e., from 80 mg TID to 40 mg TID) once. Special attention should be paid to neurological symptoms such as delirium/psychosis, gait disturbance/ataxia, and peripheral neuropathy. A grade 2 toxicity of the above neurological symptoms should prompt a consideration for further work-up and dose reduction. No second dose reduction is allowed—if a second dose reduction is required, DSF and Cu will be discontinued and the patient will be taken off study. Of note, hematologic toxicity is uncommon for DSF and is likely related to TMZ.

##### **6.2.1 Administration of DSF to Patients with Abnormal Hepatic Function**

DSF-Cu should only be administered if hepatic function is within the parameters established in the eligibility criteria. Hepatic toxicity from DSF-Cu is uncommon but may occur. Therefore, hepatic dysfunction that occurs while the patient is on study should prompt an evaluation to determine the cause, including the possibility of hepatotoxicity from concurrent medications.

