## 3.0 PATIENT SELECTION

### 3.1 Inclusion Criteria

1. At least 18 years of age.
2. Diagnosis of histologically confirmed GBM (WHO grade IV). Subjects with an original histologic diagnosis of low grade glioma or anaplastic glioma (WHO grade II or III) are eligible if a subsequent histological diagnosis of GBM is made.
3. The subject must have completed RT with concurrent TMZ at least 3 months prior to the planned start of treatment on this study UNLESS there is pathological verification of recurrent GBM and at least 4 weeks have elapsed since the end of RT with concurrent TMZ.
4. Experienced first unequivocal progression of GBM by magnetic resonance imaging (MRI) [as assessed via Radiologic Assessment in Neuro-Oncology (RANO) criteria] within 3 months from the last dose of TMZ.
5. Recent resection of recurrent or progressive tumor will be allowed as long as at least 2 weeks have elapsed from the date of surgery and the subject has recovered from the effects of surgery. Evaluable or measurable disease following resection of recurrent tumor is mandated for eligibility into the study.
6. Karnofsky performance status (KPS) of at least 70% (see Appendix A).
7. Willing to remain abstinent from consuming alcohol while on DSF.
8. Recovered from the toxic effects of prior therapy to < grade 2 toxicity per NCI CTCAE version 4 prior to study registration (except lymphopenia). The minimum duration required between prior therapy and initiation of study drug treatment is as follows:
  - a. 12 weeks from completion of radiation therapy UNLESS there is histological confirmation of tumor recurrence in which case at least 4 weeks from completion of RT will suffice

- b. 4 weeks from prior cytotoxic therapy
  - c. 4 weeks from prior experimental drug
  - d. 6 weeks from nitrosoureas
  - e. 3 weeks from procarbazine
  - f. 1 week for non-cytotoxic agents, such as interferon, tamoxifen, and cis-retinoic acid
9. Meets the following laboratory criteria:
- a. Absolute neutrophil count  $\geq$  1,000/mcL
  - b. Platelets  $\geq$  75,000/mcL
  - c. Hemoglobin  $>$  10.0 g/dL (transfusion and/or ESA allowed)
  - d. Total bilirubin and alkaline phosphatase  $\leq$  2x institutional upper limit of normal (ULN)
  - e. Aspartate aminotransferase (AST) and alanine aminotransferase (ALT)  $<$  3 x ULN
  - f. Blood urea nitrogen (BUN) and creatinine  $<$  1.5 x ULN
10. Able to take oral medication.

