### 4.1 Pretreatment Evaluation

Prior to enrollment, patient must have a complete history, physical examination including neurological exam, evaluation of performance status using the KPS, assessment of corticosteroid usage (mg per day), baseline laboratory studies (CBC, BMP, and LFTs), and brain MRI. A baseline MRI scan must be performed within 21 days prior to registration. Women of childbearing potential must have a negative pregnancy test within 14 days of initiation of treatment.

**Commented [SM2]:** Is this really necessary? It may mandate additional costly MRI's.

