#### 4.4 Study Evaluations

Consistent with institutional standard of care, patients will be seen approximately every 4 weeks and typically within 10 days before the start of the next cycle. At each visit, a KPS evaluation and corticosteroid usage (mg per day) will be recorded. Brain MRI will be obtained every 8 weeks to assess for radiological response.

Patients are evaluated for adverse events for 30 days from the last treatment of DSF-Cu, or until death, whichever occurs first. Patients removed from study for unacceptable adverse events will be followed until resolution or stabilization of the adverse event.

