#### **4.7 Duration of Therapy**

If at any time the constraints of this protocol are considered to be detrimental to the patient's health and/or the patient no longer wishes to continue protocol therapy, the

protocol therapy should be discontinued and the reason(s) for discontinuation documented in the case report form.

In the absence of treatment delays due to adverse events, DSF treatment may continue until:

- Documented and confirmed disease progression
- Death
- Adverse event(s) that, in the judgment of the investigator, may cause severe or permanent harm or which rule out continuation of study drug
- General or specific changes in the patient's condition render the patient unacceptable for further treatment in the judgment of the investigator
- Suspected pregnancy
- Serious noncompliance with the study protocol
- Lost to follow-up
- Patient withdraws consent
- Investigator removes the patient from study
- The sponsor (Cantex), the investigator, or the investigator's institution decides to close the study

In the case of tumor progression, both TMZ and DSF-Cu should be discontinued, and patient should be considered for second-line therapy. If TMZ is temporarily withheld due to toxicity, DSF-Cu should be continued until TMZ may be resumed again. If TMZ is discontinued, DSF-Cu may be continued as per the discretion of the treating physician. If DSF-Cu is discontinued due to toxicity, TMZ may be continued as per the discretion of the treating physician.

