## 10.0 STUDY CALENDAR

Screening/baseline evaluations are to be conducted within 2 weeks prior to start of protocol therapy. Scans and x-rays must be done no more than 4 weeks prior to the start of the protocol therapy. Each treatment cycle is 28 days.

	Screening / Baseline	Within 10 Days Before Each Cycle	End of Every Even-Numbered Cycle	End of Treatment	Follow-Up 
Informed consent	X				
H&P incl. neurologic exam, KPS	X	X		X	
Evaluation of corticosteroid usage	X	X			
CBC	X				
LFTs	X				
Brain MRI	X		X 	X	
Temozolomide		Days 1-5 of each cycle 			
Disulfiram		Days 1-28 of each cycle 			
Copper gluconate		Days 1-28 of each cycle 			
AE assessment	X ----- X 				

1. Follow-up will be as clinically indicated. A chart review will be done at 2 years after the last dose of DSF to look for progression and survival.
2. Women of childbearing potential only.
3. A confirmatory MRI should be considered in 4-8 weeks after documentation of complete response (CR) or partial response (PR) if consistent with the institutional standard of care
4. To be taken at bedtime on an empty stomach. Must not be taken within an hour of DSF.
5. To be taken three times a day with meals.
6. AEs will be tracked for 30 days after the last dose of DSF.

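### Section 6.2.1 relies on liver function results during treatment, but no liver function test is scheduled after Screening/Baseline, so asymptomatic hepatic toxicity is found and tabulated only if a site tests in routine care

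*Combined protocol and SAP*

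**What the plan says.** Section 6.2.1, which stands under Dose Modifications, makes two statements. The first is that "DSF-Cu should only be administered if hepatic function is within the parameters established in the eligibility criteria". The second is that "hepatic dysfunction that occurs while the patient is on study should prompt an evaluation to determine the cause". It also describes hepatic toxicity from DSF-Cu as uncommon but possible.

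The limits it refers to are in Section 3.1, criterion 9: total bilirubin and alkaline phosphatase at or below 2 x ULN, and AST and ALT below 3 x ULN.

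On testing, Section 4.1 requires "baseline laboratory studies (CBC, BMP, and LFTs), and brain MRI" before enrollment. For visits on treatment, Section 4.4 says "At each visit, a KPS evaluation and corticosteroid usage (mg per day) will be recorded", adds an MRI every 8 weeks, and names no laboratory test. In the Section 10.0 calendar the LFT row has one mark, under Screening/Baseline. The column "Within 10 Days Before Each Cycle" is marked for "H&P incl. neurologic exam, KPS" and for corticosteroid use, but not for LFTs.

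Section 6.2 allows one 50% reduction of DSF for any non-hematologic toxicity of grade 2 or higher that is at least possibly related to DSF. Section 12.2 tabulates DSF-related toxicities by type and CTCAE grade.

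**The concern.** A rule stated in terms of AST, ALT, bilirubin and alkaline phosphatase can act during treatment only if those values are measured during treatment. On a literal reading of the schedule they are not. A patient could pass the 3.1 limits without symptoms, stay on DSF-Cu, and never receive the evaluation that 6.2.1 asks for. The hepatic laboratory part of the 6.2 rule has the same gap.

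Reporting is also affected. Safety and tolerability of DSF-Cu given three times daily with temozolomide (TMZ) is the first secondary objective (Section 2.2). If testing is left to each site of a multi-center trial, the absence of hepatic laboratory toxicity from the Section 12.2 table could mean that none occurred or that nobody tested.

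**Working it through.** **1. Rule against schedule.**

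| What needs a result | Where | LFT scheduled to supply it |
|---|---|---|
| Hepatic limits for giving DSF-Cu, read as a condition for starting | 6.2.1, first sentence; 3.1 | Yes, baseline (4.1, 10.0) |
| The same limits, read as continuing | 6.2.1, first sentence; 3.1 | None |
| Evaluation of hepatic dysfunction on study | 6.2.1, on-study clause | None |
| Grade 2 or higher rule, hepatic laboratory part | 6.2 | None |
| DSF-related toxicity table, hepatic laboratory part | 12.2 | None |

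LFTs scheduled after baseline: 0.

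**2. Could this be a flaw in the calendar as it reads?** The calendar is imperfect: footnote 2 (women of childbearing potential) has no matching row. However, the H&P, corticosteroid and MRI rows keep several marks each, and the prose of 4.4 independently names no laboratory test on treatment. A lost mark is unlikely.

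**3. How often would it matter?** The documents give no rate of asymptomatic elevation. What they give is indirect:
- Table 2 lists hepatitis as rare, 1% or less. At 1%, 20 patients give 20 x 0.01 = 0.2 expected events and a probability of at least one of 1 - 0.99^20 = 0.18. Asymptomatic elevation may be commoner than hepatitis, but no figure is given.
- Table 1 (Section 1.6) lists no hepatic event among the grade 2-3 toxicities possibly or probably related to DSF in 7 + 5 = 12 phase I patients on 500-1000 mg DSF with TMZ. The one-sided 95% upper bound for 0 of 12 is 1 - 0.05^(1/12) = 0.221. That study's LFT schedule is not stated.
- Section 1.6 reports grade 3 LFT abnormality among the toxicities of DSF alone at 250-500 mg, without a patient count. The dose here is 80 mg x 3 = 240 mg per day, with copper 1.5 mg x 3 = 4.5 mg per day and TMZ.

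**4. What would scheduled testing cost?** Assume exponential PFS, treatment until progression and 28-day cycles. Let S be the probability of remaining progression-free over 28 days. The mean number of pre-cycle visits after cycle 1 is S + S^2 + ... = S/(1 - S). Add one panel at end of treatment.
- Historical rate (Section 1.2, median PFS 7.5 weeks = 52.5 days): S = exp(-28 x ln 2/52.5) = 0.691, and 0.691/0.309 = 2.24. Total 3.24 per patient, or 65 in 20 patients. The same curve gives PFS6 = exp(-182.6 x ln 2/52.5) = 0.090, which agrees with the reported 9%.
- Target (Section 12.1, PFS6 30%): daily rate = -ln(0.30)/182.6, S = 0.831, S/(1 - S) = 4.93. Total 5.93 per patient, or 119 in 20 patients.

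An end-of-treatment panel may coincide with a pre-cycle one, so these totals are slightly generous.

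**The case against.** The strongest case is that no rule is broken. The first sentence of 6.2.1 points back to the eligibility criteria and can be read as a condition for starting, which the baseline LFTs meet. The on-study clause is reactive and sets no explicit duty of surveillance. The calendar does not look like a complete list of clinical laboratory tests either: CBC also has only a baseline mark although TMZ is given every cycle, and the BMP required in 4.1 has no row. Visits follow institutional standard of care (4.4) and TMZ changes follow routine care (6.1), so bloods may simply have been left to routine practice.

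The risk also looks low. Active or severe hepatic disease and known hepatitis C are excluded, and alcohol abstinence is required. Section 1.7 reports that 250 mg DSF with 6 mg copper daily was well tolerated in patients with advanced liver metastasis, and that 500 mg DSF with 2 mg copper three times daily has been well tolerated to date. Long-term high-dose DSF in rats showed no liver damage.

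Much of this stands. The start-of-treatment reading is open, routine care may supply the results, and the expected frequency is low. What remains is the on-study clause, which has no scheduled trigger for a change without symptoms. The documents do not say how often sites test, and TMZ-related bloods cannot be relied on throughout, since "If TMZ is discontinued, DSF-Cu may be continued as per the discretion of the treating physician".

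A reader might go further and infer three things that the documents do not support:
- *On-study toxicity goes unmonitored.* Neurological toxicity, the main DSF concern, is covered by the scheduled pre-cycle neurologic exam. Symptomatic hepatic events can be caught at visits and by continuous AE assessment, and abnormal results from routine care can be recorded as AEs (7.1).
- *The 22% bound points to a moderate hepatic risk.* It reflects 12 patients and no observed events. It shows only that a moderate rate is not excluded.
- *DSF-Cu must be held above the limits.* Section 6.2 permits a reduction and contains no mandatory hepatic hold. That is a clinical decision.

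**Conclusion.** The point holds as a mismatch between a stated safety rule and the schedule meant to serve it. Section 6.2.1 expects hepatic dysfunction on study to be evaluated, and the hepatic laboratory part of the 6.2 rule expects it to be graded. With no LFT scheduled after baseline, an asymptomatic change is found and tabulated only through testing that the protocol does not require. This holds even if the first sentence of 6.2.1 applies only at the start of treatment. It rests on the calendar marks being read correctly, which the prose of 4.4 supports.

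The number of events missed cannot be estimated and is probably small. The consequence is for individual patient safety and for how a hepatic zero in the 12.2 table can be interpreted. It does not touch N, the error rates or the co-primary analyses. It is a cheap improvement that should be made.

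**What to change.** - Mark LFTs in the pre-cycle and end-of-treatment columns of the Section 10.0 calendar.
- Add them to Section 4.4 and to the CRF. Allow routine-care results within the visit window to be used.
- State in Section 6.2.1 that a value beyond the 3.1 limits prompts the evaluation already described there. Leave any hold or resumption rule to the clinical team.

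The cost is an amendment to these sections and the CRF, plus about 3 to 6 routine panels per patient (about 65 to 119 in 20 patients) under the exponential assumption, less whatever routine care already provides. The draws fall at visits already held about every 4 weeks, in a trial that already plans research blood at Week 2 and after 1 month (Section 9.0). Acting on the results might lead to a few dose interruptions and so slightly alter exposure to DSF-Cu. N and the co-primary analyses are unchanged.

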##### **6.2.2 Hypersensitivity Reactions**

Hypersensitivity reactions rarely occur. If they do occur, minor symptoms such as flushing, skin reactions, dyspnea, lower back pain, hypotension, or tachycardia may require no intervention; however, severe reactions, such as hypotension requiring treatment, dyspnea requiring bronchodilators, angioedema, or generalized urticaria require immediate discontinuation of study drug administration and aggressive symptomatic therapy. Patients who experience a severe hypersensitivity reaction to DSF should discontinue DSF immediately and not be re-challenged.

### **7.0 REGULATORY AND REPORTING REQUIREMENTS**

#### **7.1 Adverse Events (AEs)**

**Definition:** any unfavorable medical occurrence in a human subject including any abnormal sign, symptom, or disease.

**Grading:** the descriptions and grading scales found in the revised NCI Common Terminology Criteria for Adverse Events (CTCAE) version 4.0 will be utilized for all toxicity reporting. A copy of the CTCAE version 4.0 can be downloaded from the CTEP website:

[http://ctep.cancer.gov/protocolDevelopment/electronic\\_applications/ctc.htm](http://ctep.cancer.gov/protocolDevelopment/electronic_applications/ctc.htm).

**Attribution (relatedness), Expectedness, and Seriousness:** the definitions for the terms listed that should be used are those provided by the Department of Health and Human Services' Office for Human Research Protections (OHRP). A copy of this guidance can be found on OHRP's website:

<http://www.hhs.gov/ohrp/policy/advevntguid.html>

## 7.2 Unanticipated Problems

### **Definition:**

- unexpected (in terms of nature, severity, or frequency) given (a) the research procedures that are described in the protocol-related documents, such as the IRB-approved research protocol and informed consent document; and (b) the characteristics of the subject population being studied;
- related or possibly related to participation in the research (in this guidance document, possibly related means there is a reasonable possibility that the incident, experience, or outcome may have been caused by the procedures involved in the research); and
- suggests that the research places subjects or others at a greater risk of harm (including physical, psychological, economic, or social harm) than was previously known or recognized.

## 7.3 Noncompliance

**Definition:** failure to follow any applicable regulation or institutional policies that govern human subjects research or failure to follow the determinations of the IRB. Noncompliance may occur due to lack of knowledge or due to deliberate choice to ignore regulations, institutional policies, or determinations of the IRB.

## 7.4 Serious Noncompliance

**Definition:** noncompliance that materially increases risks, that results in substantial harm to subjects or others, or that materially compromises the rights or welfare of participants.

## 7.5 Protocol Exceptions

**Definition:** A planned deviation from the approved protocol that are under the research team's control. Exceptions apply only to a single participant or a singular situation.

Protocol exceptions are not expected or encouraged, and should be discussed first with the Study Sponsor.

#### **7.6 Reporting to the Institutional IRB**

The PI is required to promptly notify the IRB of the following events:

- Any unanticipated problems involving risks to participants or others which occur at WU, any BJH or SLCH institution, or that impacts participants or the conduct of the study.
- Noncompliance with federal regulations or the requirements or determinations of the IRB.
- Receipt of new information that may impact the willingness of participants to participate or continue participation in the research study.

These events must be reported to the IRB within **10 working days** of the occurrence of the event or notification to the PI of the event. The death of a research participant that qualifies as a reportable event should be reported within **1 working day** of the occurrence of the event or notification to the PI of the event.

